3.3 Study Duration, Enrollment and Number of Sites

3.3.1 Duration of Study Participation

Total study duration for each participant is approximately 12-14 months. Participants will have 6-12 months of active treatment. If there is a delay in treatment (brief hospitalization or cancelation of an appointment due to weather, illness, etc.) treatment duration may be slightly longer. It is anticipated that all treatment will be complete within 12-14 months of enrollment.

Adolescents and their families will be assessed at five time points:

- T₁: neuropsychological assessment, therapy session, questionnaires, Grocery store (parents), Buffet challenge (adolescent)
- T₂: therapy session, questionnaires
- T₃: neuropsychological assessment, questionnaires
- T₄: neuropsychological assessment, questionnaires, Grocery store (parents), Buffet challenge (adolescent)
- T₅: questionnaires, neuropsychological assessment, Grocery store (parents), Buffet challenge (adolescent)

- T₆: Medical chart review and questionnaires (to be completed online/ mailed to the family, this will take place 3 months post end of primary treatment intervention)
- T₇: Medical chart review and questionnaires (to be completed online/ mailed to the family, this will take place 6 months post end of primary treatment intervention)

3.3.2 Total Number of Study Sites/Total Number of Subjects Projected

The study will only be conducted at Children's Hospital of Philadelphia.

It is expected that approximately 60 subjects will be enrolled to produce at least 45 evaluable subjects.

3.4 Study Population

3.4.1 Inclusion Criteria (Adolescent)

1. Age 12-18
2. Currently meets DSM-5 criteria for Anorexia Nervosa
3. Medically stable for outpatient treatment
4. Fluent in English
5. No co-morbid condition that would exclude participation (diagnosis of a pervasive developmental disability or mental retardation, psychosis, bipolar disorder, substance abuse, or autism spectrum disorder)
6. Medical clearance from primary care physician and permission to speak to PCP about clinical issues
7. Biological parents or primary caregivers willing to engage in treatment and who live with the adolescent.

3.4.2 Inclusion Criteria (Parents)

1. Age >18
2. Child with a diagnosis of AN
3. Both parents willing to participate
4. Fluent in English
5. No co-morbid condition that would exclude participation

3.4.3 Exclusion Criteria (Adolescent)

1. Outside of age range
2. Adopted
3. No more than four sessions of prior CRT in any format
4. Presence of: pervasive developmental disability, psychosis, bipolar disorder, substance abuse, autism spectrum disorder, or intellectual disability.
5. Presence of: a brain disorder or injury (such as TBI) that could impact the ability to engage in treatment
6. Use of anti-psychotic medication during first 15 FBT sessions. Use of this medication is permitted in the optional 12 FBT sessions in the 6-month follow-up period of this study. This medication can affect cognitive abilities, which may interact with assessments that measure cognitive flexibility. However, we do not measure cognitive flexibility in the 6-month follow-up period when the 12 additional FBT sessions can take place.

7. Concurrent psychosocial therapy

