1.2.2 Cognitive Remediation Therapy

CRT is an adjunctive intervention focusing on the development of meta-cognition – teaching individuals to think about how they think.⁴⁴ It involves presenting individuals with a variety of

tasks requiring increasingly complex mental abilities – these include geometric figures, illusions, reversing sequences of numbers and letters, completing sorting tasks wherein the rules change, and finding various routes on a map.⁴⁵ Most importantly, CRT focuses on process instead of outcome. That is, instead of focusing on whether or not a task was accurately completed, individuals in CRT are asked to think about how they solved a puzzle, reflect on their thought processes, and identify steps in problem solving. CRT has three goals:

1. Improve brain function by exercising and increasing connections in the brain
2. Encourage individuals to think about their thinking style
3. Encourage individuals and families to spend time away from thinking about the eating disorder.

CRT can be delivered in individual, family, and group formats.⁴⁶⁻⁴⁸ For this study, we will administer CRT to either adolescents or their parents. CRT will be delivered for 45-60 minutes prior to FBT sessions for a total of 15 sessions. Participants in CRT will be given weekly homework.

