2.1 Primary Objective (or Aim)

Aim 1: To identify whether or not it more impactful to add a parent or adolescent component of CRT to standard FBT. We hypothesize that both adolescents and parents who receive CRT will have greater increases in cognitive flexibility than those who receive FBT alone. We will examine magnitude of change in cognitive flexibility across groups.

Aim 2: To determine the dose of CRT needed to lead to a medium effect size (increase in cognitive flexibility). We will examine the dose of CRT needed to obtain an increase in cognitive flexibility equal to a medium effect.

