3.4.4 Exclusion Criteria (Parents)

1. Presence of: pervasive developmental disability, psychosis, bipolar disorder, substance abuse, autism spectrum disorder, or intellectual disability.
2. Presence of: a brain disorder or injury (such as TBI) that could impact the ability to engage in treatment
3. Use of anti-psychotic medication during first 15 FBT sessions. Use of this medication is permitted in the optional 12 FBT sessions in the 6-month follow-up period of this study. This medication can affect cognitive abilities, which may interact with assessments that measure cognitive flexibility. However, we do not measure cognitive flexibility in the 6-month follow-up period when the 12 additional FBT sessions can take place.
4. No more than four sessions of prior CRT in any format

Subjects who do not meet all of the enrollment criteria will not be enrolled. Any violations of these criteria will be reported in accordance with IRB Policies and Procedures.

Patients with AN who receive psychosocial treatment at CHOP are typically followed by adolescent medicine at CHOP. Though it is possible that an adolescent will enter the trial and not be followed by CHOP's adolescent medicine, this is extremely unlikely. If it does happen, the adolescent will need to be followed by his or her pediatrician for the duration of the study and permission to speak to the pediatrician will be obtained (standard of care).

Concurrent psychosocial therapy for the adolescent is an exclusionary criterion. Given the life-threatening nature of AN, treatment for it is primary. It is standard of care for the outpatient program at CHOP to request that patients discontinue with outside therapy while receiving treatment for the eating disorder. In addition to eliminating any confounding effects of outside treatment, this practice follows the current standard of care and will be used in this study. If medication is prescribed for the adolescent it is typically done by either adolescent medicine, the adolescent's primary pediatrician, or by CHOP psychiatry. Visits with psychiatry (either within or outside of CHOP) will be allowed for medication management only. Any changes in medication will be confirmed with the prescribing physician or through the medical chart (if at CHOP) and noted.

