6 STATISTICAL CONSIDERATIONS

6.1 Primary Endpoint

Aim 1: To identify whether or not it more impactful to add a parent or adolescent component of CRT to standard FBT. To assess if CRT engages the target, we will use mixed 3 (treatment) x 2 (time) Multivariate Analysis of Covariance (MANCOVA): one for adolescents, one for mothers, and one for fathers. The covariate for all analyses is total IQ on the WASI. Dependent variables are as follows: Trails Number-Letter Sequencing, Inhibition, Inhibition/Switching, Correct Response Shifting, Category Switching, or Description 1 or 2 and Shift on the BRIEF-2. We will follow these steps:

1. Conduct omnibus MANCOVA and evaluate significance. If not significant, stop and move to next analysis.
2. If the omnibus test is significant, we will conduct individual 2 (treatment) X 2 (time) Analysis of Covariance (ANCOVA) to determine which dependent variable had significant change, with IQ again as the covariate.
3. Each assessment of the target (DV) will be examined. Results will inform the Go/No-Go Decision as described in Table 6.

These three steps will be repeated for adolescents, mothers, and fathers. We will include all three groups in the initial MANCOVA and follow-up with planned comparisons (ANCOVA) of FBT vs the appropriate CRT condition. In all analyses, we will focus on the within and between-group effects, examining interaction effects are not necessary to evaluate the target. As we have chosen measures demonstrated to change with CRT,^{40,87-90} we will maintain $\alpha=0.15$ for each analysis.⁹¹ We do not expect adolescents whose parents receive CRT or parents whose adolescents receive CRT to demonstrate increases in flexibility. However, should the planned ANCOVAs not be significant, we will be able to explore other possible group differences. Additionally, we will explore the relationship between dependent variables via discriminant analysis. These additional methods to examine the data will not factor into the Go/No-Go decision, but will enhance the depth of our understanding of the data and contribute to our understanding of neurocognition in AN.

Aim 2: To determine the dose of CRT needed to lead to a medium effect size. Some research indicates that ≥ 8 sessions of CRT are necessary for improvement in cognitive flexibility with AN.⁹² It is unknown how many sessions will be needed for significant change in parents of

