adolescents with AN. To determine optimal dose, we will model change across the 15 sessions using latent growth curve modeling (LGCM). LGCM will allow us to analyze individual and average trajectory and model linear and quadratic trend. We will visually assess for the point (dose) at which there is a significant decrease in the *rate* of improvement (quadratic). Parameter estimation will employ Maximum Likelihood (ML) estimation.^{93,94} We will evaluate model fit using chi-square (χ^2), Comparative Fit Index (CFI), Standardized Root Mean Squared Residual (SRMR), and Root Mean Squared Error of Approximation (RMSEA).⁹⁵ The following values are indicative of acceptable fit between the model and the observed data variance/covariance matrixes: CFI, SRMR, and RMSEA, $< .95$, $< .80$, and $< .05$, respectively. We will assess and compare different models using BIC and novel criteria such as Scaled Unit Information Prior BIC.^{96,97} Examining standardized model residuals in addition to global fit indices (GFI) permits us to identify model misspecification even if GFI values suggest adequate fit.⁹⁵

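### The prior-CRT item in both exclusion lists is worded with reversed polarity: taken literally it excludes people with 0–4 prior sessions and admits those with 5 or more

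*Combined protocol and SAP*

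**What the plan says.** Section 3.4.3, item 3, lists "No more than four sessions of prior CRT in any format" among the adolescent exclusion criteria. Section 3.4.4, item 4, repeats the same words among the parent exclusion criteria.

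The text after the parent list makes the criteria binding: "Subjects who do not meet all of the enrollment criteria will not be enrolled". It adds that violations are to be reported under IRB policy. It also confirms how the exclusion items are meant to work, using another item as its example: "Concurrent psychosocial therapy for the adolescent is an exclusionary criterion".

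The inclusion lists (3.4.1 and 3.4.2) do not mention prior CRT.

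**The concern.** An exclusion list works by naming what disqualifies. An item that states a permitted maximum belongs in an inclusion list; placed under an exclusion heading, it reverses its own meaning. Here the reversal affects a rule that decides who enters a trial of CRT, and it affects adolescents and parents alike.

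What is at stake is mainly the auditability of eligibility. Staff must mentally reverse the item to use it sensibly. A monitor or IRB reader who applies the text as it stands would class each CRT-naive participant as an eligibility violation and would pass a participant who had already completed a full CRT course. The documents do not say which rule screeners were told to apply.

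**Working it through.** The plan gives no figure to reproduce on this point; the check is one of logic.

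**Step 1: polarity of the lists.** In 3.4.3 the other items are being outside the age range, adoption, listed diagnoses, brain disorder or injury, anti-psychotic use during the first 15 sessions, and concurrent psychosocial therapy. In 3.4.4 they are listed diagnoses, brain disorder or injury, and anti-psychotic use. Each names a condition that keeps a person out if present. The prior-CRT item is the only one phrased as a limit to be respected.

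**Step 2: where such wording does fit.** Items beginning with 'No' appear in both inclusion lists (3.4.1 item 5 and 3.4.2 item 5, on comorbid conditions), and there the negative form works correctly. This suggests that the prior-CRT item is inclusion-style wording placed in the wrong list.

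**Step 3: apply both readings.** Let k be the number of prior CRT sessions.

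- As written under an exclusion heading: excluded if k ≤ 4.
- As a cap (evident intent): excluded if k > 4, that is, k ≥ 5.

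| k | As written | As a cap |
|---|---|---|
| 0 | excluded | allowed |
| 1 | excluded | allowed |
| 2 | excluded | allowed |
| 3 | excluded | allowed |
| 4 | excluded | allowed |
| 5 or more | allowed | excluded |

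The two rules are exact complements, so no value of k gives the same decision under both.

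**Step 4: look for a correction elsewhere.** Neither inclusion list mentions prior CRT. The screening description (3.1.1) and the recruitment section (9.5) refer to the inclusion and exclusion criteria without restating this one. Nothing resolves the polarity.

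**Step 5: formal size.** Section 3.3.2 expects about 60 enrolled. The documents do not give the distribution of k. The number of families with at least one formal violation of the literal rule therefore runs from 0 (only if every adolescent and parent had 5 or more prior sessions) to all 60 (for example, if everyone is CRT-naive). The upper end is the more plausible, since section 1.3 describes CRT research in adolescents as limited, but that is a judgement and not a figure in the plan.

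**The case against.** **It is only a drafting slip.** 'No more than' is the language of a cap, and keeping CRT-naive families out would make no sense in a trial asking whether CRT improves flexibility and at what dose. Nobody would screen that way. This stands as an account of intent, and it limits the seriousness of the point. It does not remove the point, because the wording is in operative text, it appears twice, and departures from it are reportable.

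**The binding sentence treats criteria as conditions to be met, so the item can be read as a cap.** This does not hold for the list as a whole. Read that way throughout, subjects would have to be outside the age range and adopted. The sentence cannot set the polarity of a single item.

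**A stronger reading: the trial enrolled the wrong population.** A reader might infer this, but the documents do not support it. They are silent on which rule screening used, and the sensible reading is the more likely one.

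**A second stronger reading: permitted prior sessions distort Aim 2.** A reader might note that four sessions are 4/15 = 27% of the course and 4/8 = 50% of the eight-session level that section 6.1 mentions, and infer that the dose curve is shifted. The documents do not support this either:

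- Section 6.1 models change over the 15 trial sessions, so the dose in question is that of trial-delivered CRT.
- Section 6.4 defines the effect as a rise from baseline above Family Based Treatment (FBT) alone. Baseline is taken at intake, before trial treatment (3.1.2, 3.1.3), so any lasting effect of earlier CRT on level is already in the starting value. An effect on slope is conceivable, but nothing in the plan shows one.
- Both percentages are ceilings for one participant who enters with exactly four sessions. The prevalence of prior CRT is not given; if nobody has any, the effect is nil.
- Section 6.1 attributes the eight-session figure to some research only, and says that the number needed in parents is unknown.
- Adding earlier sessions of unknown format and timing to the dose variable would mix uncontrolled exposure with protocol sessions.

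**Prior CRT goes unrecorded.** This too is an inference. Applying a four-session limit requires asking for the count. One can say only that no field for it is named in the chart-abstraction list (5.1.1), the intake list (4.1) or the medication section (4.5).

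**Conclusion.** The point holds as a correction of operative wording. In both exclusion lists the prior-CRT item, taken literally, excludes 0–4 prior sessions and admits 5 or more, which reverses the evident intent at every value. As written, each CRT-naive enrolment is formally a violation.

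The conclusion rests on reading this item with the same polarity as its neighbours; no external figure is needed. That a cap was intended is an inference from the phrasing and from the trial's purpose. The consequence is for the clarity and audit of eligibility. No design figure changes, and neither bias in Aim 2 nor enrolment of the wrong population has been shown.

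**What to change.** Reconcile heading and wording in 3.4.3 item 3 and 3.4.4 item 4. Either begin each item with 'More than four' in place of 'No more than four', or move the present wording unchanged to the inclusion lists in 3.4.1 and 3.4.2. Use the same solution for adolescents and parents.

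Confirm from the screening form or staff instructions which rule was applied, and file a short note so that enrolments made under the current text are not later counted as violations, or are identified if any truly were.

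Optionally, keep the prior-session count obtained at screening for each adolescent and parent and report it descriptively by arm. No change to the Aim 2 model is asked for.

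The cost is a one-line amendment in two lists and one check of screening practice, plus one data field if the optional step is taken.

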3.4.4 Exclusion Criteria (Parents)

1. Presence of: pervasive developmental disability, psychosis, bipolar disorder, substance abuse, autism spectrum disorder, or intellectual disability.
2. Presence of: a brain disorder or injury (such as TBI) that could impact the ability to engage in treatment
3. Use of anti-psychotic medication during first 15 FBT sessions. Use of this medication is permitted in the optional 12 FBT sessions in the 6-month follow-up period of this study. This medication can affect cognitive abilities, which may interact with assessments that measure cognitive flexibility. However, we do not measure cognitive flexibility in the 6-month follow-up period when the 12 additional FBT sessions can take place.
4. No more than four sessions of prior CRT in any format

Subjects who do not meet all of the enrollment criteria will not be enrolled. Any violations of these criteria will be reported in accordance with IRB Policies and Procedures.

Patients with AN who receive psychosocial treatment at CHOP are typically followed by adolescent medicine at CHOP. Though it is possible that an adolescent will enter the trial and not be followed by CHOP's adolescent medicine, this is extremely unlikely. If it does happen, the adolescent will need to be followed by his or her pediatrician for the duration of the study and permission to speak to the pediatrician will be obtained (standard of care).

Concurrent psychosocial therapy for the adolescent is an exclusionary criterion. Given the life-threatening nature of AN, treatment for it is primary. It is standard of care for the outpatient program at CHOP to request that patients discontinue with outside therapy while receiving treatment for the eating disorder. In addition to eliminating any confounding effects of outside treatment, this practice follows the current standard of care and will be used in this study. If medication is prescribed for the adolescent it is typically done by either adolescent medicine, the adolescent's primary pediatrician, or by CHOP psychiatry. Visits with psychiatry (either within or outside of CHOP) will be allowed for medication management only. Any changes in medication will be confirmed with the prescribing physician or through the medical chart (if at CHOP) and noted.

4 STUDY PROCEDURES

4.1 Study Intake (Visit 0)

- Informed Consent
- Medical Record Review (without participants)
- Height and weight
- Questionnaires
- Buffet Challenge
- Howe's Grocery
- Neuropsychological and IQ testing
- 2D:4D measurement
- Clinical interview (video recorded)
- Treatment sessions (audio or video recorded)

4.2 Study Treatment Phase

General overview of this phase.

4.2.1 Visit 1-8, 10-12, 14-17

Each visit the family will receive the treatment assigned during randomization (FBT, CRT_P, or CRT_A). The following will happen at each session:

- Height and weight
- Review of homework
- Study intervention
- Medical Record Review (without participants)

4.2.2 Visit 4

- Questionnaires (online or in-person)
- Height and weight
- Medical Record Review (without participants)

4.2.3 Visit 9

- Medical Record Review (without participants)
- Height and weight
- Questionnaires (online or in-person)
- Neuropsychological testing

4.2.4 Visit 13

- Medical Record Review (without participants)
- Height and weight
- Questionnaires (online or in-person)
- Buffet Challenge
- Howe's Grocery
- Neuropsychological testing

4.2.5 End of treatment evaluation (Visit 18)

- Medical Record Review (without participants)
- Questionnaires (online or in-person)
- Height and Weight
- Buffet Challenge
- Howe's Grocery
- Neuropsychological and IQ testing
- Clinical interview

4.2.6 Optional continuation of FBT

- 12 optional additional sessions of FBT

4.2.7 Visits 19 and 20

- Medical Chart Review (without participants)
- Questionnaires (online or by mail)

4.3 Permission to Speak with Physician

Appropriate **clinical** management of AN requires that the treatment team be in communication. Participants must provide consent for the study therapist to speak with the medical provider to coordinate care (e.g., the therapist will need to know when the adolescent is medically able to return to school, exercise, or sports). In order for this clinical coordination to occur, the physician **does not** have to be informed of the participant's participation in a clinical trial. Whether or not the physician is informed of study participation is at the participant's participants' discretion. As the primary treatment provided in this study is FBT and standard of care, there is no reason to expect the physician to think the adolescent is participating in a study.

4.4 Unscheduled Visits

Unscheduled visits will not be permitted. Contact with families between sessions will be as needed or on an emergent basis. Contact will be documented and must be in line with the appropriate treatment.

4.5 Concomitant Medication

All prior and concomitant medications used within 30 days prior to the screening visit and through the end of the study will be recorded. The dates of administration, dosage, and reason for use will be included.

